**Amended:**

Version	Date
Version 1	12/31/2013
Version 2	07/24/2014
Version 3	10/02/2014
Version 4	12/12/2014
Version 5	03/23/2016
Version 6	12/01/2017
Version 7	12/04/2018
Version 8	12/17/2018
Version 9	05/19/2020

**LIST OF ABBREVIATIONS**

AE	Adverse Event
ALT	Alanine Aminotransferase
AST	Aspartate Aminotransferase
AS	Active Surveillance
BUN	Blood Urea Nitrogen
CBC	Complete Blood Count
CMP	Comprehensive Metabolic Panel
CR	Complete Response
CT	Computed Tomography
CTCAE	Common Terminology Criteria for Adverse Events
DLT	Dose Limiting Toxicity
DOT	Disease Oriented Team
DSMB	Data and Safety Monitoring Board
ECOG	Eastern Cooperative Oncology Group
FDA	Food and Drug Administration
GCP	Good Clinical Practice
H&P	History & Physical Exam
HRPP	Human Research Protections Program
IHC	Immunohistochemistry
IV (or iv)	Intravenously
MRI	Magnetic Resonance Imaging
NSS	Nephron Sparing Surgery
NCI	National Cancer Institute
ORR	Overall Response Rate
OS	Overall Survival
PBMCs	Peripheral Blood Mononuclear Cells
pCR	Pathologic Complete Response
PD	Progressive Disease
PET	Positron Emission Tomography
PFS	Progression Free Survival
p.o.	per os/by mouth/orally
PR	Partial Response
RCC	Renal Cell Cancer
RECIST	Response Evaluation Criteria in Solid Tumors
SAE	Serious Adverse Event
SABR	Stereotactic Ablative Radiation Therapy
SBRT	Stereotactic Body Radiation Therapy
SRM	Small Renal Mass
SCCC	Simmons Comprehensive Cancer Center
SD	Stable Disease

SGOT	Serum Glutamic Oxaloacetic Transaminase
SPGT	Serum Glutamic Pyruvic Transaminase
WBC	White Blood Cells

**STUDY SCHEMA**

**STUDY SUMMARY**

Title	Stereotactic Ablative Radiation Therapy (SABR) for patients with primary Renal Cancer (RCC)
Short Title	SABR for primary RCC
Protocol Number	The standard protocol number used to identify this study
Phase	Phase II
Methodology	Single arm open label
Study Duration	5 years
Study Center(s)	Single-center
Objectives	To eliminate growth and viable tumor in biopsy proven small primary RCC by SABR
Number of Subjects	16
Diagnosis and Main Inclusion Criteria	biopsy proven and growing small primary RCC
Study Product(s), Dose, Route, Regimen	Stereotactic Ablative Radiation Therapy (SABR): 3 fractions of 12Gy, or 4 fractions of 10Gy or 5 fractions of 8 Gy
Duration of administration	1-3 Weeks.
Reference therapy	Lesion growth is being compared to pre-treatment growth
Statistical Methodology	Exact binomial test

## **1.0 BACKGROUND AND RATIONALE**

### **1.1 Disease Background**

The incidence of kidney cancers has been on the steady rise since 2004 with a rise of 4.1% per year [1]. In 2012 an estimated 64,770 cases diagnosed and 13,570 deaths occurred due to kidney cancers, the majority (92%) of which were renal cell cancers (RCC) [1]. This places kidney cancers within the ten highest cancers in terms of incidence as well as death. More than half of these cases were diagnosed at the local stage. The common use of ultrasound, computed tomography, and magnetic resonance imaging resulted in an increase in the incidental discovery of small renal tumors (<4 cm) [2, 3]. Surgery remains the mainstay of curative treatment for renal cell carcinomas. However, depending on patient health status and tumor size, observation and in situ tumor ablation are alternatives. The objective of surgery is to excise all tumors with an adequate normal tissue margin [2]. As such, nephron-sparing surgery (NSS), primarily in the form of partial nephrectomy, is commonly utilized as a treatment for small renal tumors. Accepted indications for NSS include presence of a solitary kidney, reduced renal function, and medical conditions with future risk for reduced renal function [4-7]. In fact, multiple studies have shown that partial nephrectomy achieved similar results when compared to radical nephrectomy in properly selected patients [4-11]. In an effort to provide the advantages of NSS while reducing its morbidity, laparoscopic and robotic partial nephrectomy has been developed [12, 13].

Ablative treatments for renal cell carcinoma, although not completely non-invasive, are currently being developed that further reduce the morbidity associated with NSS. Cryoablation and radiofrequency ablation (RFA) comprise the ablative modalities that are in clinical use [9, 14-20]. In all cases, kidney tumors are biopsied prior to or after ablation for histologic diagnosis. Unfortunately, the long-term oncologic efficacy of the ablative technologies remains unknown and no published study has reported rates of cancer-specific death, metastatic progression, or local disease recurrence after presumed successful ablation.

Conventional radiotherapy has not been used to treat primary renal tumors. Many technical challenges associated with treatment of kidney tumors including limited radiation tolerance of the normal kidneys and the surrounding tissues and difficulty of target localization have prevented routine use of radiotherapy for tumors of the kidney. However, the advent of image guided stereotactic radiosurgery system, which is completely non-invasive, has made feasible what was once technically prohibitive. Stereotactic radiosurgery has been used successfully to treat tumors of various anatomic sites including the brain, the liver, and the lung [21-23].

### **1.2 Stereotactic Ablative Body Radiation (SABR)**

Stereotactic ablative radiation therapy (SABR) also known as Stereotactic Body Radiation Therapy (SABR) is an emerging treatment paradigm defined in the American Society of Therapeutic Radiology and Oncology guidelines as a “treatment method to deliver a high dose of radiation to the target, utilizing either a single dose or a small number of fractions with a high degree of precision within the body” [24]. Potential indications for SABR include a broad spectrum of tumor types and locations. The safety and efficacy of SABR to multiple sites is excellent as documented in multiple studies [25-27].

The concept of stereotactic radiosurgery involves tightly conforming dose of therapeutic radiation confined to a small region of the body. This results in eradication or ablation of the target tumor with sparing of surrounding normal tissues. The largest experience with stereotactic radiosurgery is for the treatment of intracranial tumors. This requires a rigid immobilization device, which often is directly attached to the bony skull. Until recently,

fractionated extracranial stereotactic radiosurgery has not been possible due to many technical challenges. The critical issues include accuracy of targeting the tumor, required rapid dose fall-off away from the tumor, and adjustment for target movement during the therapy. These factors could not be addressed simultaneously until the advent of stereotactic body radiotherapy.

There are several options for delivery of stereotactic radiotherapy dose to the target volume including TrueBeam, Cyberknife and Vero. The treatment machines have several factors in common. They are able to deliver the intended dose utilizing high energy (>4 MV) X-ray photons with accurate and reproducible treatment set up. The modern linear accelerator has been successfully used to deliver stereotactic radiotherapy. A landmark study by Timmerman, et al., reported a complete response rate of 27% for patients with in-operable non-small cell lung cancer after stereotactic radiotherapy with modern linear accelerator [28]. The stereotactic body radiotherapy is not limited to any particular machine. What is critical is the ability to deliver high dose accurately and safely.

The immobilization of the patient to minimize the movement of the target organ is also an important requirement during the stereotactic radiotherapy treatment. Stereotactic radiotherapy allows rapid reduction in the delivered dose away from the target bed. This is accomplished by utilizing multiple beams to converge on the target from various coordinates. In addition, the system must allow monitoring of the target via the direct imaging of the target itself with cone-beam CT (CBCT). The combination of tightly conforming dose to the intended target as well as verification of the target position during the treatment spares significant portion of the normal tissue from high dose radiotherapy. The real time tracking of the target position and stereotactic delivery of high dose to the target have not been possible until the advent of the stereotactic treatment system.

### 1.3 Rationale

SABR has been implemented successfully in the definitive management of many cancers including in the definitive setting of primary lung and prostate cancers [28-31] and currently under investigation in many other sites including breast, pancreas and liver [32-36]. In the metastatic setting, SABR has been successfully applied to the local control of metastatic lesions in multiple organ sites including CNS, lung, liver, pancreas, prostate and bone [32, 37-39]. In renal cancers, SABR has shown efficacy ranges of 90-100% and 82-95% for CNS and extra-CNS metastasis respectively [40-44].

Despite the extensive and growing experience with SABR in multiple cancer sites, its application to primary renal cancers has been limited to few retrospective reviews and two phase I studies [45, 46]. The first retrospective study by [name] group reported treating 9 patients treated to primary tumors in the kidney ranged from 1.5cm-10cm with a median follow up of 27 months[45]. He reported 4/9 patients to be alive with all survivors having tumor sizes <3.4 cm. Their dose was 40Gy in five fractions. Only two patients experienced nausea/vomiting and no other toxicity was reported. A second retrospective study reported in ASTRO 2004 from Cabrini medical center reported treatment of 33 primary renal lesions with a local control of 94% at median follow up of 17 months (Gilson et. al. 2004). In the Karolinska Institute experience, 8 patients received SABR to primary RCC with 8Gy x5 or 10Gy x3 [46]. At 4 year follow up five patients were alive with no recurrence and one patient had a local failure at 15 months with. Median survival was 58 months. They reported no changes in creatinine levels after SABR and no toxicity. Karolinska institute followed this report with the publication of a prospective phase II study of RCC patients that treated 10 patients with primary RCC with an overall survival (OS) of 32 months and 96% grade I and grade II toxicity [47]. Lastly, a phase I dose escalation study that enrolled 15 patients at Boston has been presented in the 2013 ASTRO meeting (Kaplan et. al. 2013) that examined dose levels of 7 Gy x 3, 9 Gy x 3, 11 Gy x 3, 13 Gy x3, and 16 Gy x 3. They reported two

failures in the lower 7 and 9 Gy dose levels only. The toxicities were two patients having acute grade 1 nausea, five experiencing acute grade 1 fatigue and one patient having late grade 3 renal dysfunction.

Radiation induced renal complications can be slow and non-inflammatory. The extent of radiation induced kidney damage is related to the volume of renal parenchyma receiving radiotherapy, total dose given to the kidney, dose per treatment, and other underlying medical conditions such as diabetes and hypertension. Acute radiation nephritis can be seen months after exposure to radiotherapy [48]. The clinical symptoms related to acute radiation nephritis include hypertension, edema, proteinuria, anemia, and uremia. In standard fractionated treatment to both kidneys about 50% of the patients will develop the clinical manifestation described above a dose of 23 Gy [49]. Among the clinical symptoms, the development of hypertension is the most important prognostic sign correlated with severe morbidity and death. However, when 50% or less of a single kidney is irradiated to a high dose (>26 Gy), clinical radiation induced nephropathy is rare [49].

In this phase II trial, the volume of high dose radiotherapy (>10 Gy) will be restricted to <50% of the entire kidney. The current study will also implement fractionated stereotactic radiosurgery to treat a unilateral kidney tumor. Fractionated radiotherapy is advocated to further reduce the potential toxicity arising from a large single fraction regimen. In fact, fractionated radiotherapy has been the standard treatment for many tumors in variety of locations to reduce the toxicity associated with radiotherapy. A fractionated stereotactic regimen has the potential to reduce the normal tissue toxicity that often accompanies radiotherapy.

Successful implementation of stereotactic radiosurgery of renal tumors may become an effective and the least invasive treatment modality. This study will refine the current understanding of the image guided conformal therapy to the kidney using stereotactic body radiotherapy.

Based on the published retrospective and the two prospective phase I trials, the dose fractionations evaluated in this trial is 8Gy x 5, 10Gy x 4 and 12 Gy x 3. In a retrospective study published paper by Wersäll, et al, from the Karolinska Hospital, 50 patients with kidney cancer, both primary and metastatic, were retrospectively analyzed [50]. High rates of local control were achieved with doses ranging from 25 Gy to 45 Gy. The most common doses used were 40 Gy in 5 fractions and 45 Gy in 3 fractions. Another retrospective study used the dose of 40Gy in 5 fractions and both studies reported excellent control rate [45]. Therefore 8Gy x 5 is evaluated in this study. The 4 and 3 fraction equivalent doses to this dose levels are 10Gy and 12 Gy respectively, which are the two other dose levels included in this trial. Justification of the three fraction dose equivalent of 12Gy x 3 comes from the phase I study that did not see any failures at this level.

The study population for this trial is patients with biopsy proven primary RCC that are candidates for active surveillance (AS). Keeping patient safety in perspective, it is reasonable to offer an experimental treatment such as this to a patient population that would have otherwise been put in AS. At any sign of progression, the patients that have undergone SABR in this trial will be offered the standard of care (SOC) of radical nephrectomy, partial nephrectomy or ablation as deemed appropriate by the treating urologist—which is same as what would have been offered to them had they been in AS. The AUA defines AS patients to be those with small renal mass (SRM) with <3cm tumors. The NCCN recommends AS for patients with T1a tumors or tumors <4 cm. A number of retrospective and one prospective study reported on the natural history of SRMs [51-55]. A meta-analysis reviewed multiple retrospective studies and reported an average growth rate of 0.28 cm/year for these tumors [51]. They further reported a growth of 0.4 cm/year in the subset of patients that had biopsy confirmed RCC. Keeping clinical application in perspective, it is logical to use SABR only to tumors that are growing, since one third of the SRMs do not grow. Therefore, patients

showing growth >2mm in two scans will be enrolled and treated with SABR in this trial. The primary endpoint in this trial is local control and the hypothesis tested is that SABR to the SRMs will lead to an elimination of tumor growth. The local control will be defined using MRI or contrast CT and <4mm increase in single scan or <2.0mm increase in two different scans in the setting of an absence of radiographic indication of tumor viability will constitute local control [56]. Kidney function will be monitored closely to evaluate radiation induced kidney toxicity.

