#### 6. Adherence to Critical Organ Dose-Volume Limits

Attempts should be made to meet or be better than the normal tissue constraints listed below while observing the treatment planning priorities listed in Section 5.7.

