#### 7. Conducting planning with respect to the planning priorities (Section 5.7)

### 4.6 Planning Priorities

#### 4.6.1 Overall Strategies

Successful treatment planning criteria are listed in the previous section. In general, attempts should be made to successfully satisfy all of the criteria without deviation. In some circumstances, improvements can be made to the dosimetry plan beyond simply meeting the specified goals. In other circumstances, clinicians are faced with the prospect of not ideally meeting one or more of the criteria (i.e., accepting an acceptable deviation). In this section, we provide priorities in which a most ideal plan for protocol purposes is realized. Suggested priority of planning goals in order of importance is:

1. Respect spinal cord, cauda equine and sacral plexus dose constraints.

2. Meet dose “compactness” constraints including the prescription isodose surface coverage, high dose spillage (location and volume), and intermediate dose spillage (D2cm, and R50) as these define the “essence” of SABR.

3. Meet critical structure constraints other than those listed in 1.

The organ constraints are last in priority (except for nervous system tolerance), because they are the least validated. The “essence” of a stereotactic plan is captured mostly in the dose compactness justifying their higher priority. As an example in a case where not all goals can be met, it would be suggested to meet dose compactness goals without deviation even at the expense of a non-spinal cord normal tissue having acceptable deviation. Unacceptable deviations should be avoided in all cases. Again, these are suggested planning priorities and clinicians must use their judgment and experience in actual treatment given the variability of patient presentation and tolerance.

As an example, in some cases a target abuts a normal tissue structure with an assigned constraint. Obviously, it would be impossible to utilize the required expansions, treat to 54 Gy PTV dose, and also meet the normal tissues maximum dose constraint. With the exception of the spinal cord, the protocol allows an “acceptable” deviation such that the abutting normal tissue is allowed a maximum point dose of 105% of the prescription dose; however, the volume constraint must still be respected. As such, the dosimetry might be manipulated by falloff dose polarization so that the compactness criteria are met with an “acceptable” deviation of normal tissue constraints.

[figure not shown]

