#### Three Fractions

Serial Tissue	Volume	Volume Max (Gy)	Max Point Dose (Gy)**	Endpoint (≥Grade 3)
Spinal Cord	<0.35 cc <1.2 cc	15.9 Gy 13 Gy	22.5 Gy	myelitis
Cauda Equina	<5 cc	21.9 Gy	25.5 Gy	neuritis
Sacral Plexus	<5 cc	22.5 Gy	24 Gy	neuropathy
Esophagus*	<5 cc	17.7 Gy	25.2 Gy	stenosis/fistula
Heart/Pericardium	<15 cc	24 Gy	30 Gy	pericarditis

Great vessels	<10 cc	39 Gy	45 Gy	aneurysm
Rib	<5 cc	40 Gy	50 Gy	Pain or fracture
Skin	<10 cc	31 Gy	33 Gy	ulceration
Stomach	<5 cc	22.5 Gy	30 Gy	ulceration/fistula
Bile duct			36 Gy	stenosis
Duodenum*	<5 cc <10 cc	15.6 Gy 12.9 Gy	22.2 Gy	ulceration
Jejunum/Ileum*	<30 cc	17.4 Gy	27 Gy	enteritis/obstruction
Colon*	<20 cc	24 Gy	34.5 Gy	colitis/fistula
Ureter			40 Gy	stenosis
Renal hilum/vascular trunk	15 cc	19.5 Gy		malignant hypertension
Parallel Tissue	Critical Volume (cc)	Critical Volume Dose Max (Gy)		Endpoint (≥Grade 3)
Lung (Right & Left)	1500 cc	10.5 Gy		Basic Lung Function
Lung (Right & Left)	1000 cc	11.4 Gy	V-11Gy<37%	Pneumonitis
Liver	700 cc	17.1 Gy		Basic Liver Function
Renal cortex (Right & Left)	200 cc	15 Gy		Basic renal function

\*Avoid circumferential irradiation

\*\* "point" defined as 0.035cc or less

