**Renal Cortex (right and left combined as one)**

Specifically, the parallel functioning nephrons of the renal cortices of the kidneys (not the hilum).

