## **4.8 SABR Compliance**

### **4.8.1 Dosimetry Compliance**

RT treatment plans not meeting the “per protocol” criteria or scored as “variation acceptable” will be classified as “deviation unacceptable.” Normal tissue dose constraints are listed above. **NOTE: For the spinal cord, these are absolute limits, and treatment delivery that exceeds these limits will constitute a major protocol violation.** For the non-spinal cord tissues, acceptable deviation following the planning priorities allows a maximum point dose no more than 105% of the prescription dose while fully respecting the defined volume constraint (for serial tissues) OR exceeding the parallel tissue critical volume dose maximum by no more than 5%. Unacceptable deviation exceeds the volume constraint for serial tissues, exceeds the maximum point dose for serial tissues by more than 105% of the prescription dose, or exceeds the parallel tissue critical volume dose maximum by more than 5%.

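### Section 1.3 commits the trial to a kidney dose-volume limit that no constraint table, contour definition, planning criterion or compliance rule carries through

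*Protocol*

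**What the plan says.** Section 1.3 first reviews radiation nephropathy. It reports that clinical nephropathy is rare when half or less of a single kidney receives a high dose. It then makes a statement about this trial: "the volume of high dose radiotherapy (>10 Gy) will be restricted to <50% of the entire kidney". The same paragraph also relies on treating one kidney only and on fractionation.

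The operative sections say the following.

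- **4.7.1, constraint tables.** Apart from the ureter, each of the three tables has two renal rows: "Renal hilum/vascular trunk" and "Renal cortex (Right & Left").
- **4.7.2, contours.** The parenchymal structure is headed "Renal Cortex (right and left combined as one"). The hilum is contoured separately.
- **4.5.3.4, criterion 6.** "Attempts should be made to meet or be better than the normal tissue constraints listed below".
- **4.6.1, priorities.** "The organ constraints are last in priority (except for nervous system tolerance), because they are the least validated".
- **4.8.1, compliance.** "Normal tissue dose constraints are listed above". For parallel tissue, an acceptable deviation means "exceeding the parallel tissue critical volume dose maximum by no more than 5"%.
- **7.1.** For the kidney constraints the reader is sent to section 4.1, which defines SABR and its technical elements and holds no kidney dose limit.

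**The concern.** The sentence in 1.3 is worded as a commitment for this trial, not as a literature figure. It is also the only place where the protocol limits dose as a share of kidney volume. If nothing downstream tests it, a plan outside the limit can pass dosimetry review unnoticed.

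Kidney function, creatinine, renal perfusion and GFR after treatment are a secondary objective (2.2.3). Section 1.3 itself cites a late grade 3 renal dysfunction in the earlier 15-patient phase I study. With 16 patients, a few plans could shape the renal results. A report that repeats the 1.3 statement would then describe a safeguard that nobody had verified.

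**Working it through.** The protocol derives no figure from this limit, so there is none to reproduce. The check has two parts: whether the limit appears in any section that is acted on, and whether other scored limits enforce it indirectly.

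**1. The sections side by side**

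| Place | Structure | Volume | Dose (3 / 4 / 5 fractions) |
|---|---|---|---|
| 1.3 | Entire kidney | less than 50% | above 10 Gy, all schedules |
| 4.7.1 | Both cortices combined | 200 cc | 15 / 17 / 18 Gy |
| 4.7.1 | Renal hilum/vascular trunk | 15 cc | 19.5 / 21.5 / 23 Gy |

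No table row uses 10 Gy, a percentage of kidney volume, or one kidney alone. No whole-kidney or single-kidney contour is defined in 4.7.2, so the required structures do not give the volume that 1.3 refers to.

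**2. Does the cortex rule imply the limit?**

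The row is read here as at least 200 cc of combined cortex at or below the tabulated dose. Let C be the cortex volume per kidney, equal on both sides. C is not in the protocol and is an assumption. With the untreated side fully spared, the treated side must supply max(0, 200 − C) cc. The share of treated-side cortex allowed above the tabulated dose is 1 − max(0, 200 − C)/C.

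| Assumed C (cc) | Treated side must spare (cc) | Share allowed above 15/17/18 Gy |
|---|---|---|
| 100 | 100 | 0% |
| 125 | 75 | 40% |
| 150 | 50 | 67% |
| 175 | 25 | 86% |
| 200 or more | 0 | 100% |

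Tissue between 10 Gy and 15/17/18 Gy counts as spared in the tables but as high dose in 1.3. The cortex rule therefore sets no ceiling on the volume above 10 Gy at any assumed C. The 5% allowance in 4.8.1 raises the scored doses slightly: 15 × 1.05 = 15.75, 17 × 1.05 = 17.85 and 18 × 1.05 = 18.9 Gy.

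**3. Do the spillage criteria imply it?**

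Prescriptions are 36 Gy in 3 fractions and 40 Gy in 4 or 5 (4.2.2). 10/36 = 27.8% and 10/40 = 25.0%, so the half-prescription volume (18 or 20 Gy) lies wholly inside the volume above 10 Gy. The tightest D2cm entry, 50%, permits up to 18 or 20 Gy at 2 cm from the PTV.

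R50% is tied to the PTV, not to the kidney. With the 4.5.2 margins (0.5 cm axial, 1.0 cm craniocaudal) and a spherical mass of diameter d cm, PTV = π/6 × (d + 1)² × (d + 2). For d = 4 this is π/6 × 25 × 6 = 78.5 cc. R50% is interpolated linearly, as Note 1 to the table requires.

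| d (cm) | PTV (cc) | R50%, none / acceptable | Permitted 50% isodose volume (cc), none / acceptable |
|---|---|---|---|
| 2 | 18.8 | 4.57 / 5.61 | 86 / 106 |
| 3 | 41.9 | 4.15 / 5.15 | 174 / 216 |
| 4 | 78.5 | 3.43 / 4.66 | 270 / 366 |
| 5 | 131.9 | 3.07 / 3.95 | 405 / 521 |

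These are volumes of all tissue, including the PTV, so they do not show how much kidney is irradiated. They show that the criterion does not limit kidney volume above 10 Gy.

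**4. What does the limit refer to?**

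Section 1.3 does not say whether the entire kidney means the treated kidney or both, or whether the tumour counts. For two kidneys of equal volume V, half of one is 0.5V and half of both is V. The two readings differ by a factor of two.

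**The case against.** Several stronger readings are tempting, and the protocol does not support them.

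- **That plans are scored only against 4.7 and 4.8.** Section 4.5.3.4 requires seven criteria, including conformality, R50% and D2cm with their own deviation grades. These are real limits on dose outside the PTV. They do not enforce 10 Gy or 50%.
- **That the whole treated kidney may exceed 10 Gy without any recorded deviation.** The 100% figure needs at least 200 cc of cortex per kidney and considers one constraint in isolation. At 100 or 125 cc the cortex rule keeps the share above its own dose below half. The hilum row also restricts dose inside the treated kidney. And 10.6 requires adherence to the approved protocol and treats any departure as a deviation, so a known breach of 1.3 would be reportable.
- **That 1.3 contradicts the tables.** One plan can satisfy both. This is a stated safeguard not carried through, not two incompatible rules.
- **That the trial has no working renal protection.** Fractionation, unilateral treatment, the tabulated limits, laboratory follow-up and one-year scintigraphy all remain.

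The low rank of organ constraints in 4.6.1 is not evidence that the limit is missing. The dose-volume database planned in 4.8.2 partly anticipates the recording request, but the combined cortex contour would not give a per-kidney value.

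What remains is narrower: no written dosimetry check tests the 1.3 limit. A planner may check it voluntarily, but nothing requires it.

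**Conclusion.** The concern holds in this limited form. Section 1.3 commits the trial to a kidney dose-volume limit. The tables, contours, planning criteria and compliance rules neither contain it nor imply it, and the 7.1 cross-reference leads to a section without kidney limits. A plan that exceeds it can be scored compliant.

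The size cannot be fixed from the protocol. The 0% to 100% range rests on the assumed cortex volumes, equal kidneys, a fully spared untreated side and the stated reading of the 200 cc row. The gap itself does not depend on those assumptions, because no row or criterion works at 10 Gy or on a share of the kidney.

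The consequence is for safety oversight and for reading the renal secondary outcomes. The primary endpoint, sample size and power are untouched.

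**What to change.** Reconcile 1.3, 4.7.1, 4.7.2, 4.8.1 and the cross-reference in 7.1, so that any renal dose-volume limit the protocol states is also contoured and scored. Define the entire kidney: treated or both, tumour included or not. Which limit should apply is for the investigators, and no position is taken here.

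Record the kidney volume above 10 Gy for each patient from the stored plan, for plans already delivered as well as new ones. The report can then state how many plans met the 1.3 limit, and the changes in renal function can be read against that value.

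The cost is a wording amendment, one added contour where none exists, and one dose-volume value per plan for 16 patients.
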